## SECTION 2. Assessment and Evaluation of the Risks

For details, refer to the UK IRB's [Policy on Children in Research](#).

A. Provide justification for the participation of children as research subjects in your study.

The purpose of the study is to assess the effects of an adapted evidence-based parenting intervention on parent behaviors, child behaviors, child adherence to wearing their hearing equipment, and child speech/language outcomes. For all four outcomes, participation of the children is needed in assessment of outcomes, including videotaped tasks, parent-report measures, and measures administered directly to children. Children's direct participation in the parenting intervention is not necessary.

B. Has this research been conducted in adults? ☒ Yes ☐ No

If yes, is there any indication that the proposed research would benefit, or at least not be harmful to children?

There are 40 years of research evidence demonstrating the benefits of evidence-based parenting interventions to children and families.

C. Indicate how many children you propose to enroll in the study:

**Note:** Whenever possible, involve the fewest number of children necessary to obtain statistically significant data which will contribute to a meaningful analysis relative to the purpose of the study.

Justify this number:

Two children have already participated in Aim 3, the piloting of trial procedures. We plan to enroll 125 parent-child dyads (125 parents, 125 children; 72 dyads randomized to the intervention and 53 dyads randomized to the control condition) in the effectiveness trial, Aim 4. This number was determined by our biostatistician based on the individually-randomized trial design,  $\alpha=.05$ , the potential of clustering at the interventionist level, and the need to detect a medium-sized effect on the primary outcome (parenting behaviors).

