Participants randomized to the TAU control condition (n=53 dyads) will receive treatment as usual throughout Aim 4 (i.e., for most, this involves hearing healthcare appointments approximately every 6 months with their practice's providers, which may include nurses, care coordinators, ENT physicians, audiologists, and social workers).

Participants randomized to the intervention condition (FCU-DHH) (n=72 dyads) will be scheduled for their first FCU-DHH session with a trained parent coach within 2 weeks of completing the baseline assessment. Each FCU-DHH session will be delivered by a trained parent coach via videoconference or telephone. Between the first and second FCU-DHH sessions, the parent/caregiver will complete a FCU questionnaire (either online via REDCap survey, by mailed paper forms, or by telephone) that helps the parent coach understand more about the parent and child in the study and about their family context. Additional caregivers may also complete questionnaires if they have provided their consent to participate in the study. These assessments are part of the FCU intervention and will be used to populate the Feedback Form given to families by the parent coach in the second FCU session. The FCU questionnaire will not be included as sources of data for analysis of the study by researchers. If item responses are available from the parent/caregiver's baseline or annual assessments, they will not be re-asked in order to reduce participant burden (e.g., the PARYC items are part of the FCU questionnaire and will not be re-asked of primary participants; additional caregivers will still need to complete these items). The parent/caregiver will subsequently engage in up to 6 Family Check-Up sessions total within the next 4-5 months (total possible = 6 sessions per year). FCU-DHH sessions include one 60-minute assessment session (interview, questionnaires), one 45-minute feedback and motivational interviewing session, and up to four 60-minute skills-training sessions (focused on positive parenting skills such as focused praise, positive reinforcement, effective limit-setting, using consistent consequences).

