This pattern will continue (annual assessment for all participants + FCU-DHH sessions for FCU-DHH participants only, follow-up six months later for all participants) up to a maximum of 36 months after baseline, or until the study ends (participants enrolling after the 3/2/2023 IRB modification/approval are anticipated to end participation after the 18-month assessment). All data collection will occur remotely. This includes full (i.e. "annual") parent and child assessments at baseline (including child assessments of speech, language, and hearing for participants enrolled after the 3/2/2023 IRB modification/approval), 12-month, 24-month and 36-month follow-ups for all participants; reduced (i.e., "mid-year") parent-only assessments at 6-month, 18-month, 30-month follow-ups for all participants; and FCU-DHH sessions for only FCU-DHH participants following the baseline, 12-month, and 24-month assessments). All parents/caregivers will be compensated \$75 following the baseline assessments before 3/2/2023 (which do not include child language measures); \$100 for baseline assessments after 3/2/2023 (including child language measures) and each annual assessment, and \$50 for completing each mid-year assessment. With parental permission, each child will be allowed to select a small age-appropriate toy (stuffed animal, book, puzzle, etc.) following their participation in annual assessments to acknowledge their contribution to the study. No compensation will be provided for participation in the FCU-DHH sessions. This strategy is intended to make the intervention itself as similar as possible to what it would be if offered outside of a research protocol. At the completion of the study, Aim 4 parent participants will receive an additional payment of \$100 if all 7 sets of research assessments are completed, an additional \$75 if 6 sets of assessments are completed, an additional \$50 if 5 sets of assessments are completed, and an additional \$25 if 4 sets of assessments are completed. These amounts are intended to compensate parents for their long-term participation and keep parents engaged even if some assessments are missed.

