Aim 4 data analyses: To make trial arm (FCU-DHH vs. TAU) comparisons, we will utilize linear mixed modeling. In the models, we will utilize random effects corresponding to the interventionists, thus accounting for the possibility of clustering of outcomes from parent-child dyads who received the intervention from the same person. For the analysis of our primary outcome (parenting behaviors as measured by PARYC score at the first 6-month follow-up), a fixed effect for trial arm (FCU-DHH vs. TAU) will be the primary covariate of interest. Additional analyses for Hypotheses 1-4 will address each outcome over time (i.e., PARYC scores as well as continuous measures of child behavior, parent-report and objective adherence with HA/CI, and language development). To account for the correlation among repeated measurements from the same subject, in addition to random effects corresponding to the interventionists, we will also utilize an unstructured within-subject covariance structure. In these multilevel models, trial arm, time (categorical), and their interaction will be used as predictors, with the interaction being of primary interest. All tests will be two-sided with a 5% significance level and will be conducted in SAS Version 9.4 or higher (SAS Institute, Cary, NC). Furthermore, analyses will be based on intention-to-treat.

Principal components analysis and z-scores may be used to create composite language outcomes at each time-point due to the multiple measures proposed, which may reflect a single common trait. 100 Note that because rolling study enrollment is necessary (especially in smaller clinics), some parent-child dyads may have fewer observations than others.

We will measure potentially important predictors (e.g., sex, race, parental age, socioeconomic status, degree of hearing impairment, type of hearing rehabilitation device, baseline language development), and statistically compare the balance of the two trial arms. Secondary analyses will include these variables as covariates within the previously described models.

Prior to analyses, we will inspect variable distributions using histograms, probability plots, and residual plots. If necessary, transformations will be performed to make the variable distributions approximate a normal distribution. Alternatively, generalized estimating equations (GEE) may be utilized.

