Missing data will be examined to determine the appropriateness of results. We will statistically summarize and compare baseline demographics from subjects who dropped out of the study relative to subjects who did not drop out, and we will look at missing data patterns (e.g., differential dropout). Afterward, using results from these analyses, sensitivity analyses may be conducted following guidelines prescribed by a National Research Council (NRC) report and described in, for example, . Multiple imputation and/or inverse probability weighting may be utilized as necessary.

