## Statistical Analysis Plan

All tests will be two-sided with a 5% significance level and will be conducted in SAS. Analysis methods will account for clustering within parent coaches (i.e., statistical correlation among the outcomes from participants who share the same interventionist). Therefore, analysis of our primary outcome (parenting behaviors as measured by PARYC score at the first 6-month follow-up) will be achieved with linear mixed-effects modeling, with random effects to account for this clustering. A fixed effect for trial arm (FCU-DHH vs. TAU) will be the primary covariate of interest. Additional analyses will address each outcome over time (i.e., PARYC scores, PARCHISY scores, measures of child behavior, parent report and objective adherence with HA/CI, and language development). In longitudinal analyses, linear mixed effects modeling will be adjusted to account for the additional level of correlation among outcomes from the same subject (e.g., a random time effect or an unstructured covariance). Fixed effects will include trial arm, time (categorical or continuous variable), and their interaction, with the interaction being of primary interest. Because rolling study enrollment is necessary, some parent–child dyads may have fewer observations than others. Recommended statistical approaches will be used for missing data within interventionists (e.g., multiple imputation at the subject and cluster level). Sensitivity analyses will be considered and dictated by the type of missing data. We will measure potentially important predictors (e.g., sex, race, parental age, socioeconomic status, degree of hearing loss, type of hearing rehabilitation device, and baseline language development) and statistically compare the balance of the two trial arms. Secondary analyses will include these variables as covariates. Stratified randomization (by device type and poverty level) will be accounted for in analyses.

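### The primary model uses the 6-month PARYC alone, and no firm missing-data rule clearly reaches the TAU arm, so the intention-to-treat contrast can be biased if missingness or its handling differs by arm

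*Combined protocol and SAP*

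**What the plan says.** **Primary model.** The SAP (Statistical Analysis Plan) and the protocol (Research Procedures, Aim 4 data analyses) agree. The primary outcome is the PARYC score at the first 6-month follow-up, analysed by a linear mixed model with a trial-arm fixed effect and random effects for coaches. Neither names baseline PARYC as a covariate of this model. The SAP adds that the stratification factors, device type and poverty level, will be accounted for.

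**Population.** The protocol says that "analyses will be based on intention-to-treat".

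**Missing data, SAP.** "Recommended statistical approaches will be used for missing data within interventionists (e.g., multiple imputation at the subject and cluster level". The next sentence says that sensitivity analyses will be considered, depending on the type of missing data.

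**Missing data, protocol.** Dropouts and completers are compared on baseline demographics and missing-data patterns are examined, with differential dropout as the example. Sensitivity analyses may follow National Research Council guidance. Then: "Multiple imputation and/or inverse probability weighting may be utilized as necessary".

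**What data exist.** Families were randomised once baseline assessments were complete (Subject Children, Section 2, item C), and PARYC is listed among the baseline and annual measures. The protocol expects gaps: the completion bonus is meant to "keep parents engaged even if some assessments are missed".

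**Arms.** "72 dyads randomized to the intervention and 53 dyads randomized to the control condition". Only FCU-DHH families have a coach; TAU families complete assessments only.

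**Longitudinal model.** Both documents already plan a mixed model of PARYC over time with arm, time and their interaction.

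**The concern.** With one outcome row per dyad, a dyad that misses month 6 leaves the primary likelihood unless some other rule brings it back. The only rule phrased as a commitment is scoped to missing data *within interventionists*, and 53 of 125 dyads have none. The protocol's wider provision is optional and is to be settled after missingness has been inspected.

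The texts therefore admit three primary analyses: attenders only in both arms, imputation in FCU-DHH only, and imputation in both arms. They can give different answers from the same data, and nothing fixes the choice in advance. Arm-related missingness is plausible, because only FCU-DHH families are asked to attend coach sessions in the months before the 6-month questionnaire. What is at stake is the size of the primary effect, in either direction, and whether the reported estimate answers the intention-to-treat question.

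**Working it through.** **Inputs from the documents.** 72 FCU-DHH and 53 TAU dyads; two-sided 5% level; a medium-sized effect, with no number given.

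**Inputs assumed.** Effect 0.5 SD; PARYC SD 1; baseline to 6-month correlation ρ = 0.5 to 0.7; share missing p = 10% to 30%; baseline gap g between attenders and missing dyads = 0.57 SD. The documents give no dropout rate, correlation, ICC or power.

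**Step 1. The plan's own figure.** The total of 125 cannot be reproduced without those inputs. With effect 0.5 and no clustering, power = Φ(0.5/√(1/72 + 1/53) − 1.96) = Φ(0.80) = 78.9%. That makes 0.5 a reasonable stand-in for medium but does not confirm it. If 20% of each arm is missing and excluded (57.6 and 42.4 dyads), power is 69.5%.

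**Step 2. Shift in one arm's mean from using attenders only.** If missingness depends on baseline PARYC, the attenders' 6-month mean is too high by p × g × ρ.

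| p | ρ = 0.5 | ρ = 0.7 | share of 0.5 SD |
|---|---|---|---|
| 10% | 0.029 | 0.040 | 6% to 8% |
| 20% | 0.057 | 0.080 | 11% to 16% |
| 30% | 0.086 | 0.120 | 17% to 24% |

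The shift reaches 10% of the effect (0.05 SD) at p = 0.05/(0.57 × ρ), which is 18% missing for ρ = 0.5 and 13% for ρ = 0.7.

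**Step 3. What the shift does to the contrast at 20% missing.**
- FCU-DHH imputed, TAU attenders only, same dropout in both arms: the TAU mean is too high, so the estimate is about 0.44 to 0.42 instead of 0.50 (-11% to -16%).
- Attenders only in both arms, missingness related to baseline in FCU-DHH alone: about 0.56 to 0.58 (+11% to +16%).
- Attenders only, same mechanism and rate in both arms: the two shifts cancel and bias is about 0.
- Both arms imputed from baseline: bias is about 0.

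**Step 4. Simulation at the real arm sizes.** 72 and 53 dyads, 4,000 replicates, effect 0.5, ρ = 0.6, no coach effect, missingness logistic in baseline with slope 0.7 except in the first row. Entries are bias in SD; Monte Carlo standard error 0.003.

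| Missing TAU / FCU-DHH | attenders only | FCU-DHH imputed only | both imputed |
|---|---|---|---|
| 20% / 20%, completely at random | 0.004 | 0.004 | 0.004 |
| 20% / 20% | 0.000 | -0.078 | 0.001 |
| 20% / 10% | -0.044 | -0.085 | -0.007 |
| 30% / 15% | -0.051 | -0.110 | 0.005 |
| 30% / 30% | -0.004 | -0.118 | -0.004 |

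**Step 5. Limit of any baseline-based repair.** Steps 3 and 4 make missingness a function of baseline, so using baseline is bound to work there. If FCU-DHH missingness depends instead on the unseen 6-month score (20% missing, logistic slope 0.6), attenders only gives about 0.613 (+23%). Imputation from baseline still gives 0.559 to 0.587 (+12% to +17%). The closed form agrees: 0.2 × 0.57 = 0.114 for attenders, and 0.114 × (1 − ρ²) = 0.086 to 0.058 after imputation.

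**The case against.** A reader might infer that TAU dyads missing month 6 are dropped and that the intention-to-treat contrast is therefore biased. The documents do not support that.

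- No section says TAU dyads are dropped or left unimputed. The SAP sentence is illustrative and names subject-level as well as cluster-level imputation, and subject-level imputation needs no coach. The phrase may only mean that imputation must respect clustering.
- The SAP's sensitivity sentence and the protocol's missing-data paragraph have no arm restriction, and the protocol explicitly looks for differential dropout.
- Imputing FCU-DHH while deleting TAU is described nowhere. It is one reading of a loosely scoped sentence, and it conflicts with the protocol's intention-to-treat statement.
- Attenders-only analysis is unbiased when data are missing completely at random, or when mechanism and rate are the same in both arms (Step 4).
- A single-visit primary model is a legitimate choice, not an error.

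All of this stands, and it rules out the stronger reading. It does not supply a primary method. The subject-level wording sits inside a clause scoped to interventionists, the sensitivity sentence sets no primary analysis, and the protocol's imputation and weighting are optional. The single-visit model also leaves baseline and later PARYC scores unused for dyads that miss month 6.

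**Conclusion.** The concern holds in a conditional form. As planned, a randomised dyad with no 6-month PARYC contributes nothing to the primary model, and no firm rule clearly covers such a dyad in TAU. The contrast can be biased in either direction if missingness, or its treatment, differs by arm and is related to parenting; otherwise it need not be.

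At 20% missing the size is 11% to 16% of a 0.5 SD effect, negative under FCU-DHH-only imputation and positive under the differential attenders-only scenario. Every input except the arm sizes and significance level is assumed. If few 6-month scores are missing the issue is minor: at 10% missing the shift is 6% to 8%. This is a worthwhile, low-cost improvement to the plan, not evidence that the result is wrong.

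**What to change.** 1. **Primary estimate.** Take the 6-month arm difference from the longitudinal PARYC mixed model already planned. Include every randomised dyad with its baseline and any later PARYC. Use a baseline mean common to both arms, the stratification factors, and coach random effects only for post-baseline FCU-DHH scores, since baseline precedes coach contact. Fix time as categorical and the covariance as unstructured, as in the protocol; the SAP currently leaves both open.
2. **SAP wording.** Delete *within interventionists*. State that any imputation is done in both arms with the same predictors, with coach-level terms in FCU-DHH only.
3. **Sensitivity.** Keep the single-visit model as a sensitivity analysis. Add one named missing-not-at-random analysis, for example delta adjustment by arm, because item 1 does not remove bias when missingness depends on the unseen 6-month score (Step 5).

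**Cost.** SAP text and some programming; no new data or participants. The model has more covariance parameters and assumes missing at random given observed PARYC. In return it uses scores already collected and gains precision: for dyads with both scores, residual variance falls to roughly 1 − ρ² of its unadjusted value, which is 0.75 to 0.51 for ρ = 0.5 to 0.7.
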